7.8.2 Events of Clinical Interest

	_			
C	Confidential			

7.9 Communication of Adverse Events

An AE classified as SEVERE must conform to the legal requirements.

When a severe AE occurs, based on the classification described above, the investigator must not only record it in the appropriate page in the CRF but must notify it IMMEDIATELY to the health authorities and to the Ethical Committee; as must notify all Suspected Unexpected Serious Adverse Reaction (SUSAR).

Similarly, severe AE possibly related to the treatments in the study must be communicated by the study sponsor to the respective owners of the authorization of commercialization of the drugs used in the trial (MSD Global Safety (GS) by fax [name]).

Reporting SAE and targeted adverse events to the Sponsor
C Confidential

[figure not shown]

Table 6 Evaluating Adverse Events

An investigator, who is a qualified physician, will evaluate all adverse events as to:

V4.0 CTCAE Grading	Grade 1	Mild; asymptomatic or mid symptoms; clinical or diagnostic observations only; intervention not indicated.		
	Grade 2	Moderate; minimal, local or noninvasive intervention indicated; limiting age-appropriate instrumental ADL.		
	Grade 3	Severe or medically significant but not immediately life-threatening; hospitalization or prolongation or hospitalization indicated; disabling; limiting self-care ADL.		
	Grade 4	Life threatening consequences; urgent intervention indicated.		
	Grade 5	Death related to AE		
Seriousness	A serious a	dverse event is any adverse event occurring at any dose or during any use of Merck product that:		
	†Results in	n death; or		
	†Is life threatening; or places the subject, in the view of the investigator, at immediate risk of death from the event as it occurred (Note: This does not include an adverse event that, had it occurred in a more severe form, might have caused death.); or			
	†Results in a persistent or significant disability/incapacity (substantial disruption of one's ability to conduct normal life functions); or			
	†Results in or prolongs an existing inpatient hospitalization (hospitalization is defined as an inpatient admission, regardless of length of stay, even if the hospitalization is a precautionary measure for continued observation. (Note: Hospitalization for an elective procedure to treat a pre-existing condition that has not worsened is not a serious adverse event. A pre-existing condition is a clinical condition that is diagnosed prior to the use of a Merck product and is documented in the patient's medical history.); or			
	†Is a congenital anomaly/birth defect (in offspring of subject taking the product regardless of time to diagnosis);or			
,		cancer (that is not a condition of the study) (although not serious per ICH definition, is reportable to the ithin 24 hours and to Merck within 2 working days to meet certain local requirements); or		

	Is an overdose (whether accidental or intentional). Any adverse event associated with an overdose is considered a serious adverse event for collection purposes. An overdose that is not associated with an adverse event is considered a non-serious event of clinical interest and must be reported within 24 hours to the Sponsor and to Merck within 2 working days
	Other important medical events that may not result in death, not be life threatening, or not require hospitalization may be considered a serious adverse event when, based upon appropriate medical judgment, the event may jeopardize the subject and may require medical or surgical intervention to prevent one of the outcomes listed previously (designated above by a †).
Duration	Record the start and stop dates of the adverse event. If less than 1 day, indicate the appropriate length of time and units
Action taken	Did the adverse event cause Merck product to be discontinued?

	1	
Ì		
i		
'		
The assessme	nt of relation	ship will be reported on the case report forms /worksheets by an investigator who is a qualified physician
according to h	is/her best cli	inical judgment, including consideration of the above elements.
	15, 110. 2000 01.	Judgment, moduling constant and a tre decree ciements.

7.10Sponsor Responsibility for Reporting Adverse Events

All Adverse Events will be reported to regulatory authorities, IRB/IECs and investigators in accordance with all applicable global laws and regulations.

8.0 STATISTICAL ANALYSIS PLAN

8.1 Statistical Analysis Plan Summary

This is a non randomized phase II study designed to evaluate the ORR of Pembrolizumab rechallange after prior check point PD1/PDL1 treatment. All safety analysis will include all patients who recieved at least one dose os study drug. Primary ans secondary efficacy analysis will include all subjets

The goal of the primary analysis is to obtain an estimation of ORR. All eligible and treated patients will be included into this analysis. We hypothesize that the trial treatment with Pembrolizumab will results in an increase of the ORR. May be possible that a clinically meaningful effect may not be significant because of the low expected number of events and low power, specially for OS.

We have use a two stage design (Minimax) to estimate the trial sample size. Then we have taken into account the following statistical premises for each cohort of the study

P0: 0.05

P1: 0.15

 α : 0.05

β: 0.2

First stage: needs to document at least 1 response in 24 patients to go on to second stage.

[figure not shown]
Second Stage: needs at least 5 responses out of a total of 55 patients (including those on the first stage) to consider further study of Pembrolizumab in this context. Therefore, for each stratum a maximum of 55 patients (110 in total) will be recruited.

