Participation in this trial will be dependent upon supplying tumor tissue from a newly obtained formalin-fixed specimen from locations not radiated prior to biopsy. The specimen will be evaluated at a central laboratory facility for expression status of PD-L1 in a prospective manner. Only subjects whose tumors express PD-L1 as determined by the central laboratory facility will be eligible for inclusion in this study. Also, it is highly recommended to send archival tumor tissue from the patient.

3.1 3.0 OBJECTIVE(S) & HYPOTHESIS(ES)Primary Objective(s) & Hypothesis(es)

- To evaluate the efficacy of Pembrolizumab re-challenge administered 200 mg iv every 21 days in second or further line for advanced NSCLC after progression tocheck point PD1 / PDL1 inhibitors measured by Overall Response Rate (ORR) per RECIST v1.1 and per modified RECIST(irRC).

Hypothesis: Patients that have exhibit benefit to check point PD1 / PDL1 inhibitors may benefit from further Pembrolizumab therapy at the time of progression. The degree of benefit may depend on the initial response to previous check point PD1 /PDL1 inhibitors and its duration, and to the intercalation (or not) of any additional treatments such as chemotherapy among those patients without benefit to check point PD1/PDL1 inhibitors.

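### Section 8.1 words the primary analysis as one ORR over all patients, while hypotheses, stage rules and sample size are set per cohort; the plan should name the cohort-level ORR as primary.

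*Combined protocol and SAP*

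**What the plan says.** Section 8.1 (Statistical Analysis Plan Summary) describes the primary analysis in two places. One says "Primary ans secondary efficacy analysis will include all subjets". The other says "The goal of the primary analysis is to obtain an estimation of ORR. All eligible and treated patients will be included into this analysis". Neither mentions a cohort. The hypothesis that follows is directional only: "We hypothesize that the trial treatment with Pembrolizumab will results in an increase of the ORR". It gives no reference rate and no threshold.

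The same section then sizes the trial: "We have use a two stage design (Minimax) to estimate the trial sample size", and "Then we have taken into account the following statistical premises for each cohort of the study". The premises are P0 0.05, P1 0.15, alpha 0.05 and beta 0.2. The rules are "First stage: needs to document at least 1 response in 24 patients to go on to second stage" and "Second Stage: needs at least 5 responses out of a total of 55 patients (including those on the first stage"), with at most 55 patients per stratum and 110 in total.

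The primary objective in 3.1 is ORR on re-challenge, without reference to cohorts. The hypothesis under it does anticipate differences: "The degree of benefit may depend on the initial response to previous check point PD1 /PDL1 inhibitors and its duration", and also on whether other treatment was given in between. Section 5.1.1 defines the cohorts. Cohort 1 progressed on the inhibitor or less than 12 weeks after stopping it, and then had at least 4 courses of chemotherapy. Cohort 2 progressed more than 12 weeks after stopping, with no treatment in between.

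**The concern.** The estimate and the decision rule sit at different levels. An analyst who follows the primary-analysis sentence literally would report one proportion over both cohorts. The plan gives that proportion no null value, alternative or success threshold. It would be a mixture of two populations that the protocol itself expects may respond differently, and the mixing weights would depend on which cohort stopped early.

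A single headline ORR could be read as evidence of activity in both cohorts when only one supplied it. The trial is sized to answer the question for each cohort, and no readable passage says that the primary ORR is reported that way or how two cohort decisions combine into a trial conclusion.

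**Working it through.** **1. The plan's own figures.** Inputs from 8.1: P0 = 0.05, P1 = 0.15, alpha = 0.05 (taken as one-sided, since the plan does not say), beta = 0.2, n1 = 24, n = 55. With a1 the number of responses needed to continue and a the number needed at the end,

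P(success | p) = Σ over x ≥ a1 of P[Bin(24, p) = x] × P[Bin(31, p) ≥ a − x].

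| Rule | P(success) at 5% (alpha) | P(success) at 15% (power) | P(stop at 24) at 5% |
|---|---|---|---|
| ≥1/24, ≥5/55 (as written) | 0.134 | 0.920 | 0.29 |
| ≥2/24, ≥6/55 | 0.048 | 0.802 | 0.66 |

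The written boundaries do not reproduce alpha 0.05 and power 0.80. Boundaries one response higher do. If both cohorts are at 5%, the chance of at least one false-positive cohort is 1 − (1 − 0.134)² = 0.25 as written and 1 − (1 − 0.048)² = 0.09 with the higher boundaries.

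**2. Weights in an all-patient ORR.** If both cohorts reach 55, each carries 55/110 = 50%. If one stops at 24, the other carries 55/79 = 70%. With true ORRs of 5% in Cohort 1 and 15% in Cohort 2, Cohort 1 stops while Cohort 2 continues in about 29% of trials (written rules) or 59% (≥2/24, ≥6/55). The all-patient ORR then averages 10.4% or 10.7%, against 10.0% at equal weights.

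**3. Examples that need no assumed true rate.**
- 9/55 and 3/55: all-patient 12/110 = 10.9%, exact 95% CI 5.8% to 18.3%. The second cohort has 3/55 = 5.5% (CI 1.1% to 15.1%) and misses 5/55.
- 10/55 and 0/24: all-patient 10/79 = 12.7%, CI 6.2% to 22.1%, although the second cohort stopped at stage 1.

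**4. How often this could happen.** This step needs a test that the plan does not contain. I assumed an exact one-sided binomial test of the all-patient ORR against 5% at level 0.05. At 110 patients it needs at least 10 responses (P = 0.049 at 5%; 9 responses would give 0.100). I enumerated two independent cohorts, each allowed to stop at 24, with Cohort 1 at a true ORR of 5%. The table gives the probability that the all-patient ORR excludes 5% while Cohort 1 fails its own rule.

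| True ORR, Cohort 2 | Rules as written | ≥2/24, ≥6/55 |
|---|---|---|
| 5% | 0.01 | 0.02 |
| 10% | 0.21 | 0.27 |
| 15% | 0.56 | 0.65 |

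At 15%, the all-patient ORR excludes 5% in 0.69 of trials under either set of rules.

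**The case against.** The strongest defence is that 8.1 never says the cohorts are pooled or combined. The sentence about eligible and treated patients can be read as an analysis set applied within each cohort, since it comes shortly after sentences on the safety and efficacy sets. The only success statement, whether to consider further study, is tied to the 55-patient rule and so is made per cohort: a failing cohort fails whatever the other does. Section 1.0 also describes two groups, and the 3.1 hypothesis mentions intercalated treatment. All of this stands. It shows that the cohort-level reading is probably intended, but not that it is written.

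A reader might infer that the primary analysis has no hypothesis at all, or that the plan lets a failed cohort be declared positive. The documents do not support either. P0 and P1 exist for each cohort, and no passage draws a conclusion from a combined ORR. What is missing is a null value and threshold for an all-patient ORR.

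The probabilities in step 4 are not error rates of the plan. They come from an added test and fall quickly as Cohort 2 moves towards 5%. At 5% and 15% the mixture ORR really is above 5%, so excluding 5% is correct for the mixture. The error would lie in attributing it to both cohorts. The shift in the average from unequal weights is also small.

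**Conclusion.** The mismatch is real, but it is one of specification: the primary estimate is worded over all patients, while everything that gives the trial a decision is set per cohort. It does not amount to a pooled primary test, because the plan contains none.

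The arithmetic examples need no assumption about true rates, only that the primary-analysis sentence is followed literally. The frequency with which an all-patient result would mask a failing Cohort 1 runs from about 0.01 to 0.65, depending on Cohort 2's true ORR (5% to 15%), the boundaries used and the assumed 5% test. The trial's exploratory label does not remove the need for clarity, because the plan sets alpha, beta and a rule for further study.

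**What to change.** In 8.1, state that the primary analysis estimates ORR with a confidence interval, and tests it, separately in Cohort 1 and Cohort 2, each against its own two-stage rule; that conclusions are drawn per cohort; and that any all-patient ORR is descriptive and supports no conclusion. Put the same cohort wording in objective 3.1.

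Change the boundaries in the same edit. Naming the written rule as the formal test would fix alpha at 0.134 per cohort. Requiring at least 2/24 to continue and at least 6/55 for success meets the stated alpha and beta at the same 55 patients per cohort. It lowers power from 0.920 to the planned level (0.802), and a cohort at 5% then stops at 24 more often (0.66 against 0.29). The change should be made before stage 1 results are read.

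The cost is wording in two sections and a wider headline interval, based on 55 patients rather than 110. No patients, visits or data are added.

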5.6 Randomization or Treatment Allocation

Step 1. Registration

Upon signing the informed consent, patients will be registered, and a sample of the tumor will be shipped and evaluated for PD-L1 expression at the central laboratory.

All patients will be required to submit a tumor sample for PD-L1 IHC expression. If the sample is inadequate for analysis, another sample could be provided. If a new sample cannot be obtained, archival tissue can be sent. Other cases could be consulted with the trial chair.

If PDL1 status cannot be assessed by the central laboratory in the archival or newly obtained sample (not enough tissue available, not concluding result, etc.) patients with previous PDL1 positive analyzed before stating the trial, can be evaluated by Trial Chair to grant the inclusion of the patient in the study.

Detailed instructions for tissue collection, processing and shipment are provided in the samples manual.

Step 2. Central Tumor Confirmation

Confirmation of PD-L1 status will be provided by the central laboratory in 7 working days (DAKO IHC 22C3) if possible.

Step 3. Treatment Allocation

The confirmation of PD-L1 (\geq 1%) expression must be available before proceeding with the Pembrolizumab treatment. The patient's written informed consent to undergo screening for the clinical trial must be given prior to the performance of any protocol laboratory/imaging tests that are not part of local routine guidelines.

Once patients are confirmed to be eligible they will be automatically enrolled.

A maximum of 110 eligible patients will be enrolled.

[figure not shown]

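### Section 8.1 names a Minimax design, but 24/55 is not the Minimax design for its inputs (30/52 is), and these sizes meet the stated error limits only with boundaries other than those printed

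*Combined protocol and SAP*

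**What the plan says.** Section 8.1 (Statistical Analysis Plan Summary) holds the only derivation of the trial's size. It names the method: "We have use a two stage design (Minimax) to estimate the trial sample size". The inputs apply separately to the two cohorts: "Then we have taken into account the following statistical premises for each cohort of the study". They are P0 0.05, P1 0.15, alpha 0.05 and beta 0.2; whether alpha is one- or two-sided is not stated.

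The stage rules are "First stage: needs to document at least 1 response in 24 patients to go on to second stage" and, for the final analysis, "needs at least 5 responses out of a total of 55 patients (including those on the first stage". The total is then presented as a consequence: "Therefore, for each stratum a maximum of 55 patients (110 in total) will be recruited". Section 5.6 carries the same ceiling: "A maximum of 110 eligible patients will be enrolled". Section 5.6 does not name the design, so it inherits the figure and is not a second instance of the fault.

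**The concern.** A Minimax two-stage design is, by definition, the one with the smallest maximum sample size that satisfies both error limits. If a smaller qualifying design exists, the name and the numbers cannot both be right. A statistician who rebuilds the design from the name and the four inputs then arrives at a different interim size, maximum and total from those in the plan.

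The name also matters because the boundaries in the same paragraph do not deliver the stated alpha. A reader trying to recover the intended rule would turn to the design name, and it points to a different design.

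**Working it through.** **Inputs (Section 8.1).** p0 = 0.05, p1 = 0.15, alpha = 0.05 (one-sided assumed, as is usual for this type of design), power = 1 − 0.2 = 0.80. Sizes: n1 = 24, N = 55. Total: 2 × 55 = 110, which reproduces.

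**Formulas.** A cohort continues if stage 1 responses X1 exceed r1, and succeeds if total responses exceed r.

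- P(success | p) = Σ over x > r1 of P(X1 = x) × P(Y ≥ r + 1 − x), with X1 ~ Bin(n1, p) and Y ~ Bin(N − n1, p). This is the type I error at p0 and the power at p1.
- Early stopping under P0: PET0 = P(X1 ≤ r1 | p0).
- Expected size under P0: EN0 = n1 + (1 − PET0) × (N − n1).

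**Search.** Exact binomial enumeration of (n1, r1, N, r), requiring type I error ≤ 0.05 and power ≥ 0.80, finds no qualifying design with N ≤ 51. The smallest N is 52. The smallest EN0 of all (the Optimal design) occurs at N = 56. At N = 55 the qualifying design with the smallest EN0 does have n1 = 24, with r1 = 1 and r = 5.

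| Design | Continue | Success | Alpha | Power | PET0 | EN0 |
|---|---|---|---|---|---|---|
| Minimax 30/52 | ≥2/30 | ≥6/52 | 0.0430 | 0.802 | 0.554 | 39.8 |
| Optimal 23/56 | ≥2/23 | ≥6/56 | 0.0500 | 0.800 | 0.679 | 33.6 |
| 24/55 with r1 = 1, r = 5 | ≥2/24 | ≥6/55 | 0.0483 | 0.802 | 0.661 | 34.5 |
| 24/55 as printed | ≥1/24 | ≥5/55 | 0.1344 | 0.920 | 0.292 | 45.9 |

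**The last two columns for 24/55.**

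- As printed (r1 = 0): PET0 = 0.95^24 = 0.292, so EN0 = 24 + 0.708 × 31 = 45.9.
- With r1 = 1: PET0 = 0.95^24 + 24 × 0.05 × 0.95^23 = 0.292 + 0.369 = 0.661, so EN0 = 24 + 0.339 × 31 = 34.5.

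**Could other inputs give 24/55 as Minimax?** None of those tried does.

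- Alpha 0.025, beta 0.2: 42/67.
- Alpha 0.10, beta 0.2: 29/44.
- Alpha 0.10, beta 0.10: 39/60.
- A 5% dropout allowance on 52 gives 52/0.95 = 54.7, which rounds up to 55. But Section 8.1 states no allowance, and this would not turn a stage 1 of 30 into 24.

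**Size of the difference.** 55 − 52 = 3 per cohort; 110 − 104 = 6 in total; 6/104 = 5.8%.

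**The case against.** The best defence is that nothing is wrong with the sizes. With boundaries of at least 2/24 and at least 6/55, the design meets both error limits. Against 30/52 it stops an inactive cohort early more often (0.66 against 0.55) and expects about 5 fewer patients under P0 (34.5 against 39.8). The plan prints its stage sizes and thresholds, so no one has to rebuild the design from its name to run the trial. By itself the label changes no error rate, estimate or conclusion.

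Most of this stands. A reader might infer that the trial is underpowered or that 110 is an invalid total; the figures support neither. A reader might also infer that the plan enrols more patients than the named design would. With the boundaries just given, that is true of the maximum only, since the expectation under P0 runs the other way.

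The defence fails in one respect. The favourable figures, 0.66 and 34.5, belong to boundaries that the plan does not contain. Under the printed rule, early stopping under P0 is 0.292, expected size is 45.9 and alpha is 0.134. The sizes can be defended only together with a change of boundaries.

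**Conclusion.** The label is wrong. For the stated inputs the Minimax design is 30/52 (104 in total), and 24/55 is neither Minimax nor Optimal. Taken alone, this is a minor fault: an incorrect name and 3 extra patients at maximum per cohort.

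It carries more weight beside the boundaries. 24/55 meets the stated limits with at least 2/24 and at least 6/55 (alpha 0.0483, power 0.802). The printed rule gives a type I error of about 13.4% per cohort against the stated 5%. A reader might conclude that deleting one word settles the matter. It does not, because the rule left behind would still miss alpha.

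The printed thresholds of 1 and 5 equal the r1 and r of the valid design, which suggests that stop-at-or-below limits were written down as continue-at-or-above limits. That is an inference; the documents do not say so.

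The conclusion rests on two assumptions: that alpha is one-sided (0.025 does not give 24/55 either), and that the figure missing from Section 8.1 holds no further derivation. The method, all four inputs, both sizes and the total are legible.

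**What to change.** **Low-cost option.** Keep 24/55 and the total of 110. In one edit to Section 8.1:

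- delete the word Minimax and describe a two-stage design lying between Minimax (30/52) and Optimal (23/56);
- set the boundaries to continue at ≥2/24 and success at ≥6/55;
- state that alpha is one-sided;
- report alpha 0.0483, power 0.802, early stopping under P0 0.66 and expected size under P0 34.5 per cohort.

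This leaves the enrolment figures in Sections 1.0, 2.3 and 5.6 untouched. It does change the go/no-go rule in each cohort, so it is more than a wording correction and should be made before the stage 1 results are known.

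**Alternative.** Adopt the design that the plan names: n1 = 30, N = 52, continue at ≥2/30, success at ≥6/52, 104 in total (alpha 0.043, power 0.802). This saves 3 patients per cohort at maximum. It delays the interim look from 24 to 30 patients, raises expected size under P0 by about 5 per cohort compared with 24/55 at ≥2/24 (39.8 − 34.5 = 5.3), and requires the total to be amended wherever 110 appears. It is a trade-off that the sponsor may choose; the power of 24/55 does not require it.

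### Both two-stage response thresholds are one too low for the stated error rates: the written rule has a 13.4% type I error per cohort, not 5%

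*Combined protocol and SAP*

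**What the plan says.** The design is in the combined protocol and SAP, section 8.1 (Statistical Analysis Plan Summary). It is introduced with "We have use a two stage design (Minimax) to estimate the trial sample size". The inputs are P0 0.05, P1 0.15, alpha 0.05 and beta 0.2, and they apply to each cohort separately: "Then we have taken into account the following statistical premises for each cohort of the study".

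The decision rule has two parts:

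- Interim: "First stage: needs to document at least 1 response in 24 patients to go on to second stage".
- Final: "Second Stage: needs at least 5 responses out of a total of 55 patients (including those on the first stage". Meeting it means that pembrolizumab merits further study in this setting.

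The sample size follows from this: "for each stratum a maximum of 55 patients (110 in total) will be recruited". No other section restates or changes the thresholds.

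**The concern.** In a two-stage design of this kind, tables and software normally report the largest number of responses that still counts as failure at each stage. Success needs one more. Section 8.1 words 1 and 5 as minimum counts for success. If they are in fact failure boundaries, both hurdles are one response too low.

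This matters because the rule determines whether a cohort stops at 24 and whether re-challenge is put forward for further study, and because its error rates are the only justification given for 55 patients per cohort. If the thresholds are too low, an inactive cohort is declared promising more often than the plan says, and is less often stopped early.

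**Working it through.** **Inputs, all from section 8.1.** p0 = 0.05, p1 = 0.15, alpha = 0.05 (taken as one-sided), power = 1 − 0.2 = 0.80, first stage n1 = 24, total n = 55, so second stage n2 = 31.

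**Formula.** Let a1 be the minimum number of responses needed to continue and a the minimum total needed for success. Then

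P(success | p) = Σ over x from a1 to 24 of P(X1 = x) × P(X2 ≥ a − x), with X1 ~ Bin(24, p) and X2 ~ Bin(31, p).

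At p0 this is the type I error, and at p1 it is the power.

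**Step 1: reproduce the stated figures.** A search over all boundary pairs at 24/55 finds exactly one with alpha ≤ 0.05 and power ≥ 0.80: fail if ≤1 in 24, fail if ≤5 in 55. That is a1 = 2, a = 6. At p0 = 0.05:

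| x | P(X1 = x) | P(X2 ≥ 6 − x) | product |
|---|---|---|---|
| 2 | 0.22324 | 0.06712 | 0.01498 |
| 3 | 0.08616 | 0.20075 | 0.01730 |
| 4 | 0.02381 | 0.46340 | 0.01103 |
| 5 | 0.00501 | 0.79609 | 0.00399 |
| ≥6 | 0.00096 | 1 | 0.00096 |

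The sum is 0.0483. The same sum at p1 = 0.15 is 0.8023. So 24 and 55 do match the stated inputs, with 1 and 5 as failure boundaries.

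**Step 2: the rule as written** (a1 = 1, a = 5), at p0 = 0.05:

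| x | P(X1 = x) | P(X2 ≥ 5 − x) | product |
|---|---|---|---|
| 1 | 0.36883 | 0.06712 | 0.02476 |
| 2 | 0.22324 | 0.20075 | 0.04482 |
| 3 | 0.08616 | 0.46340 | 0.03993 |
| 4 | 0.02381 | 0.79609 | 0.01895 |
| ≥5 | 0.00597 | 1 | 0.00597 |

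The sum is 0.1344. At p1 = 0.15 it is 0.9200.

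**Step 3: would moving one threshold be enough?**

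| Continue if | Success if | Type I error | Power |
|---|---|---|---|
| ≥1/24 | ≥5/55 (as written) | 0.1344 | 0.9200 |
| ≥1/24 | ≥6/55 | 0.0549 | 0.8456 |
| ≥2/24 | ≥5/55 | 0.1097 | 0.8596 |
| ≥2/24 | ≥6/55 | 0.0483 | 0.8023 |

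Only moving both brings alpha to 0.05 or below with power of at least 0.80. Ignoring the interim stop does not rescue the written rule: ≥5/55 as a single stage has alpha 0.1397 and power 0.9302.

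**Step 4: early stopping and expected size.**

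- P(stop at stage 1 | 5%): P(X1 = 0) = 0.95^24 = 0.292 as written; P(X1 ≤ 1) = 0.292 + 0.369 = 0.661 with ≥2/24.
- P(stop at stage 1 | 15%): 0.020 as written; 0.106 with ≥2/24.
- Expected N at 5% = 24 + 31 × (1 − P(stop)): 24 + 31 × 0.708 = 45.9 as written; 24 + 31 × 0.339 = 34.5 corrected. The difference is about 11 patients per inactive cohort.

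**Step 5: two cohorts.** If both are inactive and independent, the chance of at least one false positive is 1 − (1 − 0.1344)² = 0.251 as written and 1 − (1 − 0.0483)² = 0.094 corrected.

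**Step 6: the Minimax label.** Searching over all stage sizes for the same inputs, the smallest feasible maximum is 52 (fail if ≤1/30, fail if ≤5/52; alpha 0.0430, power 0.8020). The 24/55 design meets the error limits but is not the minimax design.

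**The case against.** The strongest reply is that the study is exploratory, that section 8.1 names estimation of the response rate as the goal of the primary analysis, and that success only leads to further study, so a lenient rule may be acceptable or even intended. It is true that the final threshold does not alter the response-rate estimate. But a rule chosen to be lenient would have to be described as one, and the plan states 0.05 and 0.2. Either the thresholds or the error rates are wrong.

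Several qualifications do stand:

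- The documents do not show how 1 and 5 were obtained. The boundary slip is an inference, though a strong one, since these are the digits of the only feasible pair at 24/55. The mismatch does not depend on it.
- The 11-patient difference assumes that accrual pauses at 24 until responses are known. Section 8.1 mentions no pause; without one the difference shrinks.
- The plan sets alpha per cohort and claims no control across the two, so 25.1% against 9.4% is context and not a separate error.
- Confidence intervals do not separate the two rules. The exact 95% interval includes 5% both for 5/55 (3.0% to 20.0%) and for 6/55 (4.1% to 22.2%).
- The Minimax label is a minor point. The 24/55 design has a smaller expected size under the null than the true minimax design (34.5 against 39.8).

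**Conclusion.** The concern holds. The written rule has a type I error of 0.134 per cohort, 2.7 times the stated 0.05, and power of 0.920 instead of 0.80. Both thresholds are one response below the only pair that meets the stated inputs with 24 and 55 patients. The result is exact and uses only figures printed in section 8.1. It assumes independent binomial responses, a one-sided alpha, and that the stratum in the closing sentence of 8.1 means the cohort. Reading alpha as two-sided would widen the gap. This should be corrected, because a decision threshold and the error rates that justify it contradict each other.

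**What to change.** Check the original design output, then amend section 8.1 in one of two ways.

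1. **Preferred.** First stage: continue only with at least 2 responses in 24 patients (stop at 1 or fewer). Second stage: at least 6 responses in 55 patients (5 or fewer is not of further interest). State the exact type I error of 0.048 and power of 0.802 per cohort.
2. **If the present thresholds are intended.** Keep them and restate alpha as 0.13 and power as 0.92.

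In either case, drop the word Minimax and call it a two-stage design, and say whether accrual pauses at 24.

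Option 1 changes two numbers and adds no patients. Its price is that power falls from an unintended 92% to the planned 80%, and that the chance of stopping a cohort with a true 15% response rate at stage 1 rises from 2.0% to 10.6%; that loss is already counted in the 80%.

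The change should be made without reference to observed responses. If responses are already known, report the outcome under both rules, each with its true error rates.
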